## **Results**

### **Analysis of the Descriptive Statistics**

The sample comprised of 21 participants (10 male, 11 female) aged between 25 to 55 years of age.

The heart rates of the participants were normally distributed during each procedure (Table 1). This necessitated the use of parametric statistics for the analysis of heart rate.

**Table 1: Overview of Heart Rates before and after each procedure**

	N	Minimum	Maximum	Mean	Std. Deviation	Skewness		Kurtosis	
	Statistic	Statistic	Statistic	Statistic	Statistic	Statistic	Std. Error	Statistic	Std. Error
Heart Rate Before (with VR)	21	64.00	101.00	77.7143	9.64957	.878	.501	.675	.972

Heart Rate After (with VR )	21	61.00	93.00	75.9048	8.53173	.240	.501	-.518	.972
Heart Rate Before (with TA)	21	62.00	109.00	80.4286	12.35950	.465	.501	.269	.972
Heart Rate After (with TA)	21	64.00	102.00	79.0000	10.02497	.705	.501	.317	.972

In order to measure the impact of procedure on heart rate, the heart rates before and after the procedure were compared. It was observed that for both procedures the mean heart rate after the procedure was slightly lower than mean heart rate before the procedure (Table 2). However, the paired t test showed that the difference between the heart rate before and after treatment were not significantly different (Table 3).

**Table 2: Heart rate before and after the treatment for each type of procedure**

		Mean	N	Std. Deviation	Std. Error Mean
With VR	Heart Rate Before	77.7143	21	9.64957	2.10571
	Heart Rate After	75.9048	21	8.53173	1.86178
	Heart Rate Before	80.4286	21	12.35950	2.69706

With TA	Heart Rate After	79.0000	21	10.02497	2.18763
---------	------------------	---------	----	----------	---------

**Table 3: Significance of difference in heart rate before and after giving the injection for each type of procedure**

		Paired Differences					t*	Sig. (2-tailed )		
		Mean	Std. Deviation	Std. Error Mean	95% Confidence Interval of the Difference					
					Lower	Upper				
With VR	Heart Rate Before - Heart Rate After	1.80952	4.02019	.87728	-.02044	3.63949	2.063	.052		
With TA	Heart Rate Before - Heart Rate After	1.42857	6.20138	1.35325	-1.39426	4.25141	1.056	.304		

\* Calculated using the paired t test Differences are not statistically significant

The patients recorded lower heart rates while in VR than in Topical anesthetic as mentioned earlier. This was true both before and after the dental injections. However, the paired *t* test found the differences to be statistically insignificant both before and after dental injections. While when gender differences were observed it was seen that the females had a higher heart rate compared to the males in each of the four situations. It was observed that these differences were statistically significant for TA-before, VR-before and VR-after (Table 4).

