## **Statistical Analyses**

The normality of the heart rates observed was calculated and was observed to be within acceptable limits of Kurtosis and Skew. Therefore, parametric tests were used to analyze differences in heart rate. Given the subjective nature of Wong-Baker faces pain-rating scale (W-BFPS), non-parametric tests were used to analyze differences in W-BFPS.

The paired *t* test was used to compare the heart rates of the individuals between the two methods. The Wilcoxon Sign rank test was used to compare the W-BFPS between the two methods. The spearman's correlation was used to check the association between W-BFPS and heart rate for each procedure. All tests were performed at  $p<0.05$ .

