**Table 4 – Differences in Heart Rate according to Gender for each procedure**

	Gender	Mean	Std. Deviation	t*	Sig
Heart Rate Before (VR)	Male	73.4000	6.09554	-2.117	0.048**
	Female	81.6364	10.8284		
Heart Rate After (VR)	Male	73.9000	6.62403	-1.102	0.311
	Female	77.7273	9.92059		
Heart Rate Before (TA)	Male	74.9000	9.65459	-2.118	0.048**
	Female	85.4545	12.7778		
Heart Rate After (TA)	Male	74.1000	7.29459	-.2.369	0.029**
	Female	83.4545	10.3572		

\*\*Differences are significant at  $p<0.05$

A paired t test comparing the change in heart rate per procedure with the gender of the participants, showed no significance for both genders.

The patient's experience of pain with each group was measured using Wong-Baker Faces Pain-rating Scale (W-BFPS). The Wilcoxon Sign Rank test showed that while 10 of the 21 participants had a higher W-BFPS with TA when compared to VR, 5 of the 21 reported a worse experience with VR when compared to TA. There were six individuals who reported the same experience with both procedures (Table 5). These differences were however not significant ( $Z=1.662$ ,  $sig= 0.096$ )

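### The gender heart-rate text names VR-after as significant where Table 4 shows TA-after, the VR-after row is internally inconsistent, and the claim of no gender finding on change names no identifiable test

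*Combined protocol and SAP*

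**What the plan says.** - **Text before Table 4 (Results).** After stating that women had the higher pulse in all four situations, it says: "It was observed that these differences were statistically significant for TA-before, VR-before and VR-after (Table 4".
- **Table 4.** The significance flag is on VR-before (t = -2.117, p = 0.048), TA-before (t = -2.118, p = 0.048) and TA-after (p = 0.029; the t cell is malformed and read here as -2.369). VR-after has t = -1.102, p = 0.311 and no flag.
- **Text after Table 4.** "A paired t test comparing the change in heart rate per procedure with the gender of the participants, showed no significance for both genders". No mean, t, p or interval is given.
- **Statistical Analyses.** Parametric tests are used for heart rate, and the paired t test "was used to compare the heart rates of the individuals between the two methods". Wilcoxon and Spearman are the other tests named. No gender comparison and no independent-samples test is named.
- **Group sizes (Analysis of the Descriptive Statistics).** "The sample comprised of 21 participants (10 male, 11 female".

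**The concern.** There are three faults.

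1. The text names VR-after where Table 4 supports TA-after. A reader who relies on the text concludes that pulse differed by gender after VR and not after TA, which is the reverse of the table.
2. The t and p printed for VR-after do not belong together, and neither follows from the means and SDs in the same row.
3. The null statement on change does not say what was paired with what. Men and women are independent groups and cannot be paired with each other. If the test was something else, the reader cannot tell what it was, and two of the three possible meanings conflict with the document's own figures.

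The stake is limited. Gender is not among the stated aims. Pulse is, however, the only objective measure reported, and anxiety control is part of the aim, so these statements should match their tables.

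**Working it through.** **Inputs.** There are 10 men and 11 women. Table 4 gives means and SDs by gender. Table 3 gives the before-minus-after change in all 21: VR mean 1.80952, SD 4.02019; TA mean 1.42857, SD 6.20138. Tests are two-sided at 0.05.

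**Step 1: reproduce Table 4.** Pooled independent-samples test: t = (male mean - female mean) / [s_p × sqrt(1/10 + 1/11)], where s_p² = (9 × SD_m² + 10 × SD_f²)/19.

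| Row | Printed t, p | Recomputed t, p |
|---|---|---|
| VR-before | -2.117, 0.048 | -2.117, 0.048 |
| VR-after | -1.102, 0.311 | **-1.028, 0.317** |
| TA-before | -2.118, 0.048 | -2.118, 0.048 |
| TA-after | -2.369, 0.029 | -2.369, 0.029 |

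Three rows reproduce, which identifies the test. For VR-after, (73.9000 - 77.7273)/3.722 = -1.028. Welch gives t = -1.048, p = 0.309. On 19 df the printed t = -1.102 corresponds to p = 0.284, and the printed p = 0.311 needs |t| = 1.041. The VR-after means and SDs recombine to the Table 1 values (75.905, SD 8.532), so the fault lies in the t and p cells. The row is non-significant on every version.

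**Step 2: mean change by gender** (before minus after, from Table 4).
- VR: men 73.40 - 73.90 = -0.50; women 81.64 - 77.73 = 3.91.
- TA: men 74.90 - 74.10 = 0.80; women 85.45 - 83.45 = 2.00.

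**Step 3: reading (a), change in men against change in women.** Table 3 fixes the total sum of squares (SS), and the group means fix the between-gender part.
- VR: total SS = 20 × 4.02019² = 323.24. Between SS = (10 × 11/21) × 4.409² = 101.83. Within SS = 221.41, so the mean square is 221.41/19 = 11.65 and SE = sqrt(11.65 × (1/10 + 1/11)) = 1.49.
- t = 4.409/1.4915 = 2.956 on 19 df, p = 0.008. The difference is 4.41 bpm, 95% CI 1.29 to 7.53. Welch p runs from 0.008 to 0.019 over every split of the within SS that the tables allow.
- TA: total SS 769.14, within SS 761.60, difference 1.20 bpm (95% CI -4.59 to 6.99), t = 0.434, p = 0.67.

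**Step 4: reading (b), before against after within each gender.** The SDs of change by gender are not printed, but they can be bounded.
- Women, VR: if all the within SS lay in women, the SD would be sqrt(221.41/10) = 4.705. Then t is at least 3.909/(4.705/sqrt(11)) = 2.755 on 10 df, so p is at most 0.020.
- The men's SDs of pulse before and after VR (6.09554 and 6.62403) require some change in men too. That tightens the bound slightly, to 0.0197.
- Men, VR: change SD 0.53 to 4.87, p 0.015 to 0.75. Women, TA: change SD 2.42 to 8.43, p 0.021 to 0.45. Both are left open. Men, TA: change SD 2.36 to 8.84, p 0.31 to 0.78, not significant.

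**Step 5: reading (c), VR change against TA change within each gender.** Mean differences are 3.91 - 2.00 = 1.91 bpm (women) and -0.50 - 0.80 = -1.30 bpm (men). Significance would need an SD of the paired difference below 1.91 × sqrt(11)/2.228 = 2.84 (women) or 1.30 × sqrt(10)/2.262 = 1.82 (men). Those SDs are not reported, so the sentence can be neither confirmed nor refuted.

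**Step 6: how much the p = 0.008 can bear.** Multiplied by six gender tests (four in Table 4, two of change) it is 0.049. Women started VR 81.64 - 73.40 = 8.24 bpm higher, so regression to the mean may contribute. With adjustment for starting pulse and a common slope:
- within SS before 1506.9, after 1379.1; cross-product = (1506.9 + 1379.1 - 221.4)/2 = 1332.3; slope = 1332.3/1506.9 = 0.884;
- adjusted female-minus-male difference after VR = 3.827 - 0.884 × 8.236 = -3.45 bpm (95% CI -6.87 to -0.04), SE 1.624, t = -2.127 on 18 df, p = 0.047.

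**The case against.** The mislabelled comparison and the faulty row are not open to dispute. The defence concerns the sentence on change and the weight of the whole.

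- **Reading (c) may be what was meant.** It is paired, it compares changes, and it gives one result per gender. With the pooled change SDs assumed for each gender and a VR-TA correlation from -0.9 to 0.95, p is 0.24 to 0.68 for men and 0.08 to 0.52 for women, so a null result is plausible. This stands in part: on (c) the sentence may be correct. But (c) is not the natural default. The text around Table 3 uses the paired t test for before against after within each procedure, which is reading (b), and there women under VR contradict the sentence.
- **The p = 0.008 belongs to a reading that a paired test does not fit, and the multiplicity count is a choice.** This stands. Adding the four within-gender tests makes ten, and 10 × 0.0081 = 0.081. The figure should be used only to show that the sentence and the tables disagree on that reading.
- **The plan's general line on parametric tests for heart rate could cover an independent-samples test, and a footnote to Table 4 may have been lost when the PDF was read.** Both are fair. The unlisted gender analysis and the unexplained asterisk on t are missing detail and do not carry the point.
- **The consequences are small.** VR-after is non-significant either way, and the aims do not mention gender. This is true and limits the severity, but a stated conclusion that contradicts the table it cites still needs correcting.

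**Conclusion.** The concern holds. The wrong label is certain and needs no assumption: the text should name TA-after (p = 0.029), not VR-after (p = 0.311). The VR-after t and p are wrong as printed, given 10 men and 11 women and the printed means and SDs; the recomputed values are t = -1.028, p = 0.317, and the conclusion does not change.

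The sentence on change is unsupported as written. It is contradicted for VR if it means men against women (4.41 bpm, p = 0.008) or before against after within gender (women, p at most 0.020), and it is untestable if it means VR against TA within gender. For TA, nothing in the tables contradicts it.

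The figures for change rest on the Table 3 SDs being correct. They come from unplanned contrasts in 21 people with unequal starting pulse, so they do not establish a gender effect. This is a correction that should be made. It does not touch the study's main conclusions.

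**What to change.** 1. In the text before Table 4, replace VR-after with TA-after in the list of significant comparisons.
2. Recompute t and p for the VR-after row from the data, and repair the malformed t cell for TA-after.
3. State which comparison the sentence on change refers to, and give its means, SDs, t and p. If it was men against women or before against after, correct the claim for VR. If it was VR change against TA change within gender, say so and report the paired differences and their SDs.
4. If change by gender is to be discussed, use an independent-samples t test of before minus after for each procedure, with the difference and 95% CI.
5. Add a footnote naming the test in Table 4, and label all gender analyses exploratory, unplanned and unadjusted for multiplicity.

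The cost is two corrected sentences, one recomputed row, one footnote and two t tests on data already in hand.

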**Table 4 – Differences in Heart Rate according to Gender for each procedure**

	Gender	Mean	Std. Deviation	t*	Sig
Heart Rate Before (VR)	Male	73.4000	6.09554	-2.117	0.048**
	Female	81.6364	10.8284		
Heart Rate After (VR)	Male	73.9000	6.62403	-1.102	0.311
	Female	77.7273	9.92059		
Heart Rate Before (TA)	Male	74.9000	9.65459	-2.118	0.048**
	Female	85.4545	12.7778		
Heart Rate After (TA)	Male	74.1000	7.29459	-.2.369	0.029**
	Female	83.4545	10.3572		

\*\*Differences are significant at  $p<0.05$

A paired t test comparing the change in heart rate per procedure with the gender of the participants, showed no significance for both genders.

The patient's experience of pain with each group was measured using Wong-Baker Faces Pain-rating Scale (W-BFPS). The Wilcoxon Sign Rank test showed that while 10 of the 21 participants had a higher W-BFPS with TA when compared to VR, 5 of the 21 reported a worse experience with VR when compared to TA. There were six individuals who reported the same experience with both procedures (Table 5). These differences were however not significant ( $Z=1.662$ ,  $sig= 0.096$ )

**Table 5: Comparisons and Ranking of W-BFPS**

		N	Mean Rank	Sum of Ranks	Z*	Sig
W-BFPS - VR	Negative Ranks	5 a	6.50	32.50	1.662	0.096
	Positive Ranks	10 b	8.75	87.50		
	Ties	6 c				

	Total	21				
--	-------	----	--	--	--	--

a. W-BFPS - TA < W-BFPS – VR

[figure not shown]
b. W-BFPS - TA > W-BFPS – VR

c. W-BFPS - TA = W-BFPS – VR

\*calculated using the Wilcoxon Sign Rank test

Differences are not statistically significant

In contrast to the heart rate and W-BFPS reading of pain level, when patients were asked which method they preferred, a significant majority (Chi square = 14.124, p=0.021) reported that they preferred the VR to Topical Anesthesia (Fig 1).

**Fig 1:** Stated preference of procedure by the population

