# **Cover letter**

## **Comparison between the Analgesic Effectiveness of Virtual Reality and Topical Anesthesia: A Clinical Study**

**Date of document: April 28th 2021**

## **Aim**

The aims of the study are to compare the analgesic and anxiety control effectiveness of virtual reality (VR) and topical anesthesia (TA) gel during administration of local anesthesia in adult dental patients, and to determine which approach the patients preferred to reduce pain of dental injections.

The null hypothesis was that there will be no significant difference between the effect of virtual reality compared to that of topical anesthesia gel in reducing pain during administration of local anesthesia injections in adult dental patients.

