### **Patient Input**

After each procedure was performed (TA or VR), the participants were asked to evaluate the degree of pain that they experienced using the Wong-Baker Faces Pain-rating Scale (W-BFPS). Official permission was issued from the Wong-Baker FACES Foundation.

Additionally, each participant was also asked to state his/her preference of delivery system for future injections.

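### The chi-square and p-value printed for patient preference cannot belong together, and this is the only VR-versus-TA comparison declared significant

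*Combined protocol and SAP*

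**What the plan says.** The Aim section makes preference one of the study's purposes: "to determine which approach the patients preferred to reduce pain of dental injections". Under Patient Input, "each participant was also asked to state his/her preference of delivery system for future injections". That is one answer per person about two delivery systems, and the Descriptive Statistics section gives 21 participants.

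The result is in the Results text after Table 5: "a significant majority (Chi square = 14.124, p=0.021) reported that they preferred the VR to Topical Anesthesia". That sentence refers to Fig 1 and gives no counts, df or n.

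The Statistical Analyses section lists a paired t test for heart rate, Spearman's correlation between pain score and heart rate, and for pain: "The Wilcoxon Sign rank test was used to compare the W-BFPS between the two methods". It sets the 0.05 level for all tests but names none for preference.

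The other two comparisons of VR with TA were negative. For heart rate, the paired t test "found the differences to be statistically insignificant both before and after dental injections". For pain (Z = 1.662, sig = 0.096), "These differences were however not significant". The significant entries in Table 4 compare men with women, not VR with TA.

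**The concern.** A chi-square statistic and its df fix the p-value. One preference between two methods suggests df 1, or df 2 if a no-preference answer was allowed. At either, 14.124 is a very large value, while 0.021 is a modest p. The two figures describe evidence of very different strength.

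The document itself sets the preference finding against the negative pain and heart-rate results, so the one positive comparison of VR with TA rests on this pair. The stated null hypothesis concerns pain and is untouched.

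**Working it through.** **Inputs.** Chi-square 14.124 and p = 0.021 (Results, after Table 5); 21 participants (Descriptive Statistics); level 0.05 (Statistical Analyses). The df and the counts are not in the text.

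**1. Can the printed p be reproduced from the printed chi-square?** p = P(χ² with df degrees of freedom ≥ 14.124):

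| df | p at 14.124 | χ² needed for p = 0.021 |
|---|---|---|
| 1 | 0.00017 | 5.327 |
| 2 | 0.00086 | 7.726 |
| 3 | 0.0027 | 9.731 |
| 4 | 0.0069 | 11.553 |
| 5 | 0.0148 | 13.267 |
| 6 | 0.0283 | 14.906 |
| 7 | 0.0490 | 16.490 |

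The p rises with df and crosses 0.021 at df of about 5.52, so no whole number works. Rounding does not help: a p that rounds to 0.021 needs a chi-square of 13.21 to 13.33 at df 5, or 14.84 to 14.97 at df 6. Halving the p does not help either (0.0141 at df 6, 0.0245 at df 7).

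Size of the gap: 0.021 / 0.00017115 = 122.7 at df 1; 0.021 / 0.00085706 = 24.5 at df 2. Both df values are assumptions.

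**2. Can 14.124 come from these participants?** Against equal shares over k answers, χ² = k·Σnᵢ²/n − n, so n·χ² must be a whole number. At n = 21 it is 21 × 14.124 = 296.604 (296.594 to 296.615 allowing for rounding), which is not whole. No n from 2 to 21 passes, so excluding people without a preference does not rescue it. For a two-way split of 21:

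- 19:2 gives (19 − 2)²/21 = 289/21 = 13.762 (12.190 with continuity correction);
- 20:1 gives (20 − 1)²/21 = 361/21 = 17.190 (15.429 corrected).

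Two alternatives also fail to give 14.124: the likelihood-ratio chi-square for two- and three-way equal-share splits of 2 to 21 people, and every cross-tabulation of gender (10 men, 11 women) by up to three answers. A null with unequal shares is not excluded for the statistic, but step 1 would still apply to the pair.

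**3. Can p = 0.021 come from these participants?** Not from a two-way split of all 21:

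| Split | Pearson χ² | Pearson p | Exact binomial p |
|---|---|---|---|
| 15:6 | 3.857 | 0.0495 | 0.078 |
| 16:5 | 5.762 | 0.0164 | 0.0266 |
| 17:4 | 8.048 | 0.0046 | 0.0072 |

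It could arise if some people stated no preference. For example, 13/4/4 gives 3 × (169 + 16 + 16)/21 − 21 = 7.714, df 2, p = 0.0211; and 13:3, with five people excluded, gives exact p = 0.0213. These are examples, not a full list.

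**4. What depends on the answer?** Exact 95% intervals for the share choosing VR, under hypothetical counts:

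| Counts | Share for VR | 95% CI | Exact p |
|---|---|---|---|
| 19:2 (two-way split nearest the printed χ²) | 90% | 70% to 99% | 0.0002 |
| 16:5 (two-way split nearest the printed p) | 76% | 53% to 92% | 0.027 |
| 13:4 (from 13/4/4) | 76% of choosers | 50% to 93% | 0.049 |

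**5. Check on the neighbouring result.** Z = 1.662 gives two-sided p = 0.0965, which agrees with the printed 0.096 within the rounding of Z. The fault is confined to the preference sentence.

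**The case against.** The strongest reply is that no wrong conclusion has been shown. Both printed figures are below 0.05, nothing contradicts the direction in favour of VR, and the pain hypothesis is unaffected. That is correct, and the point is limited accordingly.

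Second, Fig 1 may show the counts; it is missing from the text available for this review, which is not a fault of the document. If it does, a reader could redo the test. That would show which figure is wrong, but it could not make the printed pair agree.

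Third, an exact or Monte Carlo p need not equal the chi-square tail, so the two figures might both be genuine output. This stands as a caveat, but no such method is mentioned anywhere, and for a two-way choice by all 21 the exact binomial p is never 0.021.

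Fourth, the splits in step 4 are illustrations. That all three stay below 0.05 is not a bound on what the data could show.

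**Conclusion.** The concern holds. Taking the p as the ordinary upper tail of chi-square, at least one of 14.124 and 0.021 is wrong, whatever the df. The statistic also fits no equal-share split of 21 or fewer people, whereas the p could be right if some participants expressed no preference. The evidence could therefore be anything from very strong to borderline.

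This must be corrected before the result is relied on: it is the inferential result for a stated aim. It does not show that the preference is non-significant.

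**What to change.** - **Results:** recompute from the counts behind Fig 1. Next to the test, print the numbers preferring VR, preferring TA and, if any, with no preference. Replace both printed figures with the recomputed statistic (if the chosen test has one) and p, with n and df where they apply, and add the proportion preferring VR with a 95% CI. Keep the word significant only if the p of the named test is below 0.05.
- **Statistical Analyses:** add a sentence naming the preference test, its null hypothesis, its df if it is a chi-square, and how no-preference answers are handled. A two-sided exact binomial test of VR against TA at 50% suits these numbers; a chi-square against equal shares is also valid. If all 21 chose, the exact test and the uncorrected chi-square disagree at the 0.05 level only at 15:6 (0.078 against 0.0495). The choice should be justified on method, not on the result.

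The interval and the preference for an exact test are good practice; the counts, test, df, n and corrected figures are the necessary part. The cost is minutes of re-analysis on data already held, one added sentence and one corrected sentence. No new data are needed.
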